6.3.1 Dose Adjustment Guidelines for Selinexor Related Toxicities

Toxicity will be graded according to NCI CTCAE, version 4.03; the therapy modifications described below are applied according to this severity grading.

If more than one different type of toxicity occurs concurrently, the most severe grade will determine the modification.

Re-escalation of the study drug is allowed as outlined in the sections that apply for the specific toxicity. If drug-related toxicity requires a treatment delay of more than 28 days the patient is taken off protocol treatment.

Each dose modification or treatment delay has to be documented, including the respective reason.

Table 2: Prespecified dose/schedule modifications for adverse events related to study drug

Dose level	Dose of Selinexor
Dose level 0	60 mg twice weekly (D1, D3)
Dose level -1	50 mg twice weekly (D1, D3)
Dose level -2	40 mg once weekly (D1)
Dose level -3	30 mg once weekly (D1)
Dose level -4	Discontinue dosing

Based on observations from the ongoing Phase 1 studies in patients with advanced hematological and solid tumors, we note that selinexor shows a reasonably wide therapeutic range, with activities from $\sim 10\text{mg}/\text{m}^2$ to $\geq 50\text{mg}/\text{m}^2$. Therefore, in order to optimize specific anti-tumor activity and the patient's tolerability, we will allow for dose and/or schedule modifications as described below. Patients should also be treated aggressively with supportive care to reduce toxicities.

Table 3: Criteria for dose adjustments of Selinexor-related toxicities

Toxicity and Intensity	Dose Modification
Fatigue (common)	
Grade 1	Insure adequate caloric intake and assess volume status. Adjust other medications. Consider addition of low dose corticosteroids (e.g., 4 mg dexamethasone with each dose of Selinexor or 10 mg prednisone per day every day). Rule out other causes of fatigue such as adrenal insufficiency.
Grade 2	Insure adequate caloric and fluid intake and assess volume status. Add corticosteroids on day of Selinexor (e.g., 4 mg dexamethasone), or give or 10-15mg prednisone every other day. If fatigue dose not resolve to Grade 1, increase corticosteroids to the day of and the day after Selinexor dosing, and/or reduce dose of Selinexor by one level (Table 2).

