Grade 1 (Lower Limit of Normal to 130 nM)	Maintain dose level, assure adequate fluid, electrolyte and caloric intake, adjust other medications, consider salt supplementation, rule out other causes. Be certain that reported sodium level is corrected for concurrent hyperglycemia (serum glucose $>$ 150mg/dL).
Grade 3 (120-130 nM) without symptoms	First Occurrence: Discontinue Selinexor until resolved to Grade \leq 1 then reinstate starting dose. Check renal function, serum and urinary electrolytes, and rule out other causes. Reinforce patient education regarding fluid intake. Be certain that reported sodium level is corrected for concurrent hyperglycemia (serum glucose $>$ 150mg/dL). Subsequent Occurrences: Discontinue Selinexor until resolved to Grade \leq 1 then reduce dose by 1 level (Table 2). Check renal function, serum and urinary electrolytes, and rule out other causes.
Grade 3 (120-130 nM with symptoms) or Grade 4 (<120 nM)	Check renal function, serum and urinary electrolytes, and rule out other causes. Be certain that reported sodium level is corrected for concurrent hyperglycemia (serum glucose $>$ 150mg/dL). Discontinue Selinexor until resolved to Grade \leq 1 then reduce dose by 1 level (Table 2). Check renal function, serum and urinary electrolytes, and rule out other causes.
Renal (rare)	
Serum creatinine	
Calculated or measured creatinine clearance \geq 20 cc/min	Maintain dose level
Calculated or measured creatinine clearance $<$ 20 cc/min	Maintain dose level as Selinexor is not eliminated by the kidney.
Hepatic (rare)	
Bilirubin	
Total bilirubin $<$ 1.5 x ULN	Maintain dose level
Total bilirubin 1.5-3 x ULN	Reduce Selinexor to once weekly dosing at the same dose until resolved to \leq Grade 1, then restart twice weekly dosing

Toxicity and Intensity	Dose Modification

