Grade 2 / 3	
Delay Selinexor and initiate/intensify antihypertensive therapy. Selinexor may be restarted in conjunction with standard anti-hypertensive medication if BP is controlled (i.e., BP \leq 150/100 mmHg).
 
If BP is controlled \leq 7 days after suspending Selinexor, maintain dose level
 
If BP is controlled $>$ 7 days after suspending Selinexor, then reduce by 1 dose level (Table 2).

Grade 4	
Delay the Selinexor and initiate/intensify antihypertensive therapy, then reduce by 1 dose level (Table 2).
 
Selinexor may be restarted in conjunction with anti-hypertensive medication if BP is controlled (i.e., BP \leq 150/100 mmHg).

Cardiac – Other (rare)	
Grade 1 or 2	Maintain dose level
Grade 3	Delay Selinexor until resolved to \leq Grade 1, then reduce by 1 dose level (Table 2).
Grade 4	Discontinue study treatment
Diarrhea (common)	
Grade 1 (despite maximal anti-diarrheal medication)	At the first sign of abdominal cramping, loose stools, or onset of diarrhea, it is recommended that the patient be treated according to institutional standard of care. Maintain dose level of Selinexor.
Grade 2 (despite maximal anti-diarrheal medication)	
Reduce to Selinexor to one weekly until resolved to \leq Grade 1, then re-start twice weekly at the current dose level.
 
If diarrhea returns as \geq Grade 2, then reduce Selinexor dose by one dose level and dose once weekly until resolved to \leq Grade 1, then re-start twice weekly at reduced dose level

Grade 3/4 (despite maximal anti-diarrheal medication)	Delay Selinexor until resolved to \leq Grade 1 or baseline and patient is clinically stable, then follow guidelines above.
Neurotoxicity (not observed to date)	
\geq 1 CTCAE grade level increase	
Grade 0 \rightarrow Grade 1: maintain dose level
 
Grade 0 or 1 \rightarrow Grade 2: delay study treatment until resolved to \leq Grade 1, then reduce by 1 dose level (Table 2).

\geq CTCAE Grade 3	Discontinue study treatment until resolved to Grade \leq 1 then reduce by 2 dose levels (Table 2).
Amylase and/or lipase elevations (rare)	
Grade 1 or 2	Maintain dose level

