
All dose modifications should be based on the worst preceding toxicity.
 
Isolated values of ≥ Grade 3 alkaline phosphatase values will NOT require dose interruption.
 
Determination of liver vs. bone etiology should be made, and evaluation of gamma-glutamyl transferase (GGT), 5'-nucleotidase (5'NT), or other liver enzymes should be performed.
 
Patients are allowed dose reductions to a minimum dose of 15 mg/m² as described in Table 2.
 
If a patient requires a dose interruption of > 28 days, then the patient must be discontinued from the study. Patients who discontinue the study for a study related adverse event or an abnormal laboratory value must be followed at least once a week for 28 days and subsequently at 28 day intervals until resolution or stabilization of the event, whichever comes first.
 
a. Common Terminology Criteria for Adverse Events (CTCAE Version 4.03) otherwise specified values.
	

For all ≥ Grade 3 hematological or non-hematological AEs that are NOT Selinexor related:

After consultation with the Medical Monitor and at the discretion of the treating physician, Selinexor dosing may be maintained provided that the patient can continue to take the agent by mouth, or via other enteral route.

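### For diarrhea recurring at dose level -1, Protocol Section 6.3.1 supports two Selinexor restart doses (80 or 40 mg/week), and its 15 mg/m² minimum does not fit the flat dose levels

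*Protocol*

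**What the plan says.** All references are to Protocol Section 6.3.1 unless stated. Table 2 here means the dose-level table in that section, not the schedule of assessments in Section 5.2, which carries the same number.

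- Table 2 is titled "Prespecified dose/schedule modifications for adverse events related to study drug". Levels 0 and -1 are given twice weekly (60 and 50 mg). Levels -2 and -3 are given once weekly (40 and 30 mg). Level -4 is discontinuation.
- Table 3, diarrhea grade 2, first episode: go to once weekly until grade 1 or less, "then re-start twice weekly at the current dose level".
- Table 3, diarrhea returning at grade 2 or higher: go down one level, give that dose once weekly until grade 1 or less, "then re-start twice weekly at reduced dose level". The grade 3/4 row sends the reader back to this guidance after a delay.
- Table 3, total bilirubin 1.5-3 x ULN: once weekly at the same dose until resolved, "then restart twice weekly dosing".
- General rules: "Re-escalation of the study drug is allowed as outlined in the sections that apply for the specific toxicity", and "All dose modifications should be based on the worst preceding toxicity".
- The notes to Table 3 also set a lowest dose of 15 mg/m² and cite Table 2 for it, although Table 2 holds no dose per m².

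**The concern.** A dose level in Table 2 fixes both the milligrams and the weekly frequency. The recurrent-diarrhea row takes its dose from that table but states its own restart frequency. The two agree as long as the reduced level is a twice-weekly one. They part when a patient at level -1 steps down to level -2, because Table 2 gives that level once weekly and the row restarts it twice weekly.

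At stake is a safety dosing rule with two meanings. Two sites could treat the same event differently, one giving twice the weekly dose of the other, and each could cite the protocol. Section 6.2.3 requires deviations to be recorded, and Section 8.3 assigns patients to analysis sets according to deviations, so whether a given restart counts as a deviation also depends on the reading.

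The minimum-dose note raises a smaller question of the same kind: for a large patient, level -3 is permitted by Table 2 and ruled out by the note.

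**Working it through.** **Inputs.** Doses and frequencies come from Table 2 and restart rules from Table 3. There are three dosing weeks per 4-week cycle (Section 3.1.2). The plan states no weekly totals, so there is no figure to reproduce. As a check on the reading of level 0, 2 doses x 3 weeks = 6 doses per cycle, which matches the stated total.

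**Weekly dose by level** = mg per dose x doses per week:

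- level 0: 60 x 2 = 120 mg
- level -1: 50 x 2 = 100 mg
- level -2: 40 x 1 = 40 mg
- level -3: 30 x 1 = 30 mg

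**Restart after recurrent diarrhea.** The Table 3 reading is the milligrams of the reduced level x 2. The Table 2 reading is the reduced level at its own frequency.

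| Level before | mg/week before | Table 3 reading | Table 2 reading |
|---|---|---|---|
| 0 | 120 | 50 x 2 = 100 | 50 x 2 = 100 |
| -1 | 100 | 40 x 2 = 80 | 40 x 1 = 40 |
| -2 | 40 | 30 x 2 = 60 | 30 x 1 = 30 |

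From level 0 the readings agree. From level -1 they differ by a factor of two: 80/100 - 1 = -20% against 40/100 - 1 = -60%. Per cycle that is 300 mg before, then 240 or 120 mg. From level -3 the next step is discontinuation, so no restart arises.

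**The level -2 line needs care.** The row first moves the patient to once-weekly dosing, which means something only for a patient on twice-weekly dosing. A patient at level -2 is already on once weekly, so the row does not address that case. The 60 mg/week in the table comes from applying its words literally. The first-episode diarrhea sentence and the bilirubin row have the same gap: read literally at level -2 they would turn 40 into 80 mg/week, and at level -3 30 into 60 mg/week. These are cases on which the text is silent.

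**Do the general rules decide between the readings at level -1?**

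- The re-escalation sentence defers to the section for the specific toxicity, which is the row in question.
- The worst-toxicity sentence decides which toxicity governs, not the frequency on restart.
- No statement ranks Table 2 above Table 3 or the reverse.

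**Minimum dose.** 30 mg / 15 mg/m² = 2.0 m². Above that body surface area, level -3 is under the minimum. The documents give no body surface areas and the eligibility criteria set no limit on it, so these values are assumed:

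- 2.1 m²: 30/2.1 = 14.3 mg/m²
- 2.2 m²: 30/2.2 = 13.6 mg/m²
- 2.4 m²: 30/2.4 = 12.5 mg/m²

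**The case against.** The best defence is that the toxicity row is meant to control the schedule. Section 6.3 permits flexible changes of dose, schedule or both, and the text between Tables 2 and 3 announces that such changes follow below. On that view a site takes the milligrams from the reduced level and the frequency from the diarrhea row. The row's own sequence supports this: if level -2 stayed once weekly, the temporary dose and the restart dose would both be 40 mg once weekly, and the last clause would do nothing. This defence stands far enough to make the 80 mg/week reading respectable. It does not settle the matter, because the title of Table 2 and each of its dosing entries include the schedule, and 40 mg twice weekly is not one of its levels.

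A reader might infer that the instructions cannot be followed without breaking one of them. The permission for schedule changes does not support that. A reader might also infer that the protocol orders a 50% increase after a recurrent toxicity (40 to 60 mg/week from level -2). That comes from applying a sentence to a patient it does not contemplate, and the documents do not show that it is intended.

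Two further objections are fair. The case is uncommon: Section 6.5.6 reports diarrhea in up to 27% of patients, mostly grade 1, and the row applies only when full anti-diarrheal treatment has not been enough. And the minimum-dose note is permissive in form and points to a table that already has a floor, so it looks like a unit left over from the mg/m² regimen mentioned in SAP Section 5. That origin is an inference.

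**Conclusion.** The point holds as a minor inconsistency in the dosing text. No figure in the plan is miscalculated.

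- For recurrent grade 2 or higher diarrhea at level -1, the protocol supports two restart doses, 80 or 40 mg/week after 100. Both are reductions, and both are below the 120 mg/week starting dose.
- At levels -2 and -3 the diarrhea and bilirubin rows leave a gap.
- The 15 mg/m² minimum does not match the flat levels and conflicts with level -3 above 2.0 m².

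The reach is narrow. Enrolment ended in June 2016, version 3.1 is dated 13.01.2017 and Selinexor is given for at most one year, so only patients still on the drug in the first part of 2017 can be affected by this version. The documents do not give their number. A reader might infer a threat to the trial's main result; nothing here changes the primary endpoint, alpha or power.

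**What to change.** **(a) Diarrhea, grade 2 row.** Add: Twice-weekly dosing is resumed only if the resulting level is 0 or -1; at levels -2 and -3 Selinexor is resumed once weekly as in Table 2. The medical monitor should first confirm that Table 2's schedule is what is intended, since the documents do not show it. The downside is a deeper cut from level -1 (-60% instead of -20%). If the milder cut is intended, the row should instead state 40 mg twice weekly explicitly.

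**(b) Patients already at a once-weekly level** with first-episode grade 2 diarrhea or bilirubin 1.5-3 x ULN. The medical monitor should specify the action in those two places, so that silence does not become no change by default.

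**(c) Notes to Table 3.** Replace the mg/m² minimum with: The lowest permitted dose is level -3 of Table 2 (30 mg once weekly).

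The cost is one added sentence in the diarrhea row, one clinical decision written into two places, and one replaced note. No new data, visits or patients are needed. If no patient remains on Selinexor, the clarification still helps in classifying deviations at the data review.

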6.3.2 Selinexor Dose Reduction for Decreased Glomerular Filtration Rate (GFR)

Selinexor is not significantly eliminated by the kidney. Therefore, no dose alteration of Selinexor is required with renal dysfunction.

6.3.3 Selinexor Dose Adjustment in the Setting of Infection

Patients with active uncontrolled or suspected infections should have Selinexor treatment withheld until infection has clinically resolved or the patient is clinically stabilized. After the infection has resolved clinically or the patient's clinical condition has stabilized, treatment with Selinexor may continue at the original dose. Missed doses will not be replaced. Patients may continue on antibiotics for prolonged periods while re-initiating their Selinexor regimen at the discretion of the investigator. Note: Over 1,175 patients receiving selinexor were evaluated for safety as of 31 May 2016 in clinical studies. Opportunistic infections attributed to selinexor were not observed, even with long-term (> 6-month) dosing.

6.3.4 Conditions not Requiring Selinexor Dose Reduction

The following conditions are exceptions to the above guidelines. Selinexor does not need to be held in the following cases:

- Alopecia of any grade
- Electrolyte or serum analyte (e.g., urate) abnormalities that are reversible with standard interventions

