≥ Grade 3 with bleeding	Interrupt selinexor dosing and check platelet counts weekly until the bleeding has stopped, patient is clinically stable and the platelets have recovered to Grade 2 or baseline. When resuming selinexor, reduce by 1 dose level. If the occurrence falls on a Day 1 of a cycle: delay start of cycle, check platelet counts weekly until the bleeding has stopped, patient is clinically stable and the platelets have recovered to Grade 2 or baseline. Reduce selinexor by 1 dose level when resuming.
Neutropenia	
Grade 3 or 4 Neutropenia With (febrile neutropenia) OR Without fever	Institute prophylactic antibiotics as clinically indicated per institutional guidelines. Interrupt selinexor and check neutrophils weekly until recovers to Grade 2 or baseline and without fever (if febrile) and the patient is clinically stable. Reduce selinexor by 1 dose level when resuming. If the occurrence falls on a Day 1 of a cycle: delay start of cycle, check neutrophils weekly until recovers to Grade 2 or baseline and without fever (if febrile) and the patient is clinically stable. Reduce selinexor by 1 dose level when resuming.
Anemia	
Treat per institutional guidelines including blood transfusion. Consider transfusing for haemoglobin < 8 g/dL. If possible, maintain selinexor dose as long as patient is clinically stable, but if a dose reduction or interruption is desired, consult with the Medical Monitor.	

Toxicity and Intensity	Dose Modification
Other Selinexor-related adverse events	
Grade 1 or 2	Maintain dose level and initiate standard supportive care.
Grade 3	Delay dose until resolved to ≤ Grade 1, then reduce by 1 dose level (Table 2).
Grade 4	Discontinue Selinexor and rule out other causes. If other causes of Grade 4 adverse event are uncovered, Selinexor may be re-initiated at 1 dose level reduction (Table 2).

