6.5.7 Hyponatremia

Hyponatremia Grade 3 (plasma sodium < 130 nM) has been reported in 283 patients (24%) of patients treated with selinexor as of 31 May 2016: (please note that Grade 2 hyponatremia is not recognized in the CTCAE, v. 4.03; Grade 1 hyponatremia includes any plasma level between normal and 130 nM). None of the cases of Grade 3 hyponatremia was symptomatic and all were rapidly correctable with standard measures. No instances of Grade 4 hyponatremia have been seen. One case was pseudohyponatremia due to hyperglycemia (not associated with Selinexor). Most of the patients had anorexia, nausea, vomiting and/or diarrhea. Two of the patients with Grade 3 hyponatremia had third-space fluid accumulation or resolution (e.g., ascites, edema). Adequate fluid and caloric intake, including electrolyte rich beverages rather than free water, has led to reversal of the hyponatremia.

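### Protocol Sections 6.3.3 and 6.3.4 conflict with Table 3 on handling Selinexor in Grade 3 hyponatremia and in infection with Grade 3-4 neutropenia; the passages need reconciling

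*Protocol*

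**What the plan says.** **Hyponatremia.** For Grade 3 without symptoms, Table 3 (Protocol Section 6.3.1) begins "First Occurrence: Discontinue Selinexor until resolved to Grade" 1 or better, after which the starting dose is resumed. At later occurrences it requires the same stop, followed by a one-level reduction. Section 6.3.4 then states: "The following conditions are exceptions to the above guidelines. Selinexor does not need to be held in the following cases". One of the two listed cases is "Electrolyte or serum analyte (e.g., urate) abnormalities that are reversible with standard interventions". Section 6.5.7 gives 283 patients (24%) with Grade 3 hyponatremia and adds: "None of the cases of Grade 3 hyponatremia was symptomatic and all were rapidly correctable with standard measures".

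**Infection and neutropenia.** For Grade 3 or 4 neutropenia, with or without fever, Table 3 says: "Interrupt selinexor and check neutrophils weekly until recovers to Grade 2 or baseline and without fever (if febrile) and the patient is clinically stable". The dose is then resumed one level lower. Section 6.3.3 also withholds Selinexor for active uncontrolled or suspected infection. Once the infection has resolved or the patient has stabilized, it says "treatment with Selinexor may continue at the original dose", with no neutrophil criterion.

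**Rules that bear on overlap.** Table 3 is limited to Selinexor-related toxicities. Section 6.3.1 says that, when different toxicities coincide, the most severe grade decides. After Table 3, a separate rule lets dosing be maintained, after consulting the Medical Monitor, for Grade 3 or higher events that are not Selinexor related.

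**The concern.** A protocol should give one instruction for one event. Here a site treating a patient with correctable, asymptomatic Grade 3 hyponatremia can stop Selinexor under Table 3 or continue it under Section 6.3.4, and cite the protocol either way. A site treating an infected patient with Grade 3-4 neutropenia finds two restart conditions and two restart doses.

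Patient handling and the analysis are both affected. Patients are assigned to analysis sets according to observed deviations (Protocol Section 8.3; SAP Section 7), and the per-protocol set excludes major or relevant ones (Protocol Section 8.3.2; SAP Section 7.2). If the governing instruction is not fixed, neither is the standard against which a hold, restart or reduction is judged. The SAP plans per-protocol tables of response, and it summarizes exposure and compliance by dosing schedule.

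**Working it through.** This is mainly a comparison of texts. The arithmetic only shows how often the first conflict could arise and how far apart the restart doses are.

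**1. The plan's own figure.** Section 6.5.7 gives 283 patients and 24%. Section 6.3.3 gives the safety population as over 1,175 at the same cut-off. 283 / 1,175 = 0.2409, or 24.1%, which agrees with the stated 24%.

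**2. Scaling to this trial.** Assume the pooled rate applies here, although the pooled patients are not this population.
- All 40 patients: 0.24 × 40 = 9.6, about 10.
- First 25 patients: 0.24 × 25 = 6.0.
- The 15 flat-dose patients (SAP Section 5): 0.24 × 15 = 3.6.
- At half the pooled rate, all 40 patients: 0.12 × 40 = 4.8, about 5.

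**3. The texts side by side.**

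| Event | Action | Table 3 | Other section | Conflict? |
|---|---|---|---|---|
| Asymptomatic Grade 3 hyponatremia, correctable, first occurrence | Hold | Yes | 6.3.4: not needed | Yes |
| | Dose afterwards | Starting dose | 6.3.4: no change implied | No |
| Same, later occurrence | Hold | Yes | 6.3.4: not needed | Yes |
| | Dose afterwards | One level lower | 6.3.4: no change implied | Yes |
| Infection with Selinexor-related Grade 3-4 neutropenia | Hold | Yes | 6.3.3: yes | No |
| | Restart condition | Neutrophils at Grade 2 or baseline, afebrile, stable | 6.3.3: infection resolved or patient stable | Yes |
| | Restart dose | One level lower | 6.3.3: original dose | Yes |

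**4. What the exception leaves in Table 3.** Section 6.3.4 applies when an electrolyte abnormality can be corrected by standard means. Section 6.5.7 says that was true of every Grade 3 case, and that none had symptoms. On the protocol's own description, the set of cases in the asymptomatic Grade 3 row and the set covered by the exception are essentially the same. A row with separate first-occurrence and later-occurrence rules is left with almost nothing to govern.

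**5. Whether another rule settles the infection case.** If infection and neutropenia count as two toxicities, Grade 4 neutropenia with a lower-grade infection points to Table 3. With equal grades the most-severe-grade rule is silent. If the neutropenia is attributed only to Ara-C, idarubicin or the leukemia, Table 3 does not apply. The rule for unrelated events then permits dosing to be maintained, while Section 6.3.3 still withholds for the infection. That is a third instruction.

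**6. Gap in restart dose, flat-dose patients.** The dose-level table in Section 6.3.1 gives these weekly totals in a dosing week:
- Level 0: 2 × 60 = 120 mg.
- Level −1: 2 × 50 = 100 mg.
- Level −2: 1 × 40 = 40 mg.

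After a first event the two texts lead to 120 mg (Section 6.3.3) and 100 mg (Table 3). After a second, if each text is followed throughout, they lead to 120 mg and 40 mg.

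**The case against.** The strongest reply is that precedence is stated for hyponatremia. Section 6.3.4 calls its items exceptions to what precedes it, and Table 3 precedes it. That stands, so a reader who infers that the two passages simply cancel each other goes too far. What remains is that the exception, read with Section 6.5.7, empties a detailed row. It is also permissive, so a site that holds Selinexor can still point to Table 3.

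Second, a reader might infer opposite instructions for infection as well. The documents do not support that: both texts withhold, and only the restart condition and dose differ. The limit to Selinexor-related toxicity and the most-severe-grade rule narrow the overlap further, but do not remove it. Attribution among three drugs is a judgment, and equal grades are left open.

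Third, it is tempting to say that most patients on this chemotherapy would meet the neutropenia conflict at 60 mg versus 50 mg. The documents give no rate for febrile neutropenia, not every such event is Selinexor related, and SAP Section 5 puts only 15 patients on the flat dose. No patient count can be given for this conflict.

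Fourth, version 3.1 is dated 13 January 2017 and enrolment ended in June 2016. With treatment due to start within two weeks of enrolment and induction limited to two 4-week cycles, induction should have been over before this text existed. It could direct dosing only for patients still on longer treatment. Earlier protocol versions may carry the same wording but are not available here. This limits the prospective effect, not the need to classify actions already taken.

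**Conclusion.** The point holds as a conflict of instructions. For asymptomatic Grade 3 hyponatremia, Table 3 and Section 6.3.4 disagree on holding at every occurrence, and on dose at later ones. For infection with Selinexor-related Grade 3-4 neutropenia, Table 3 and Section 6.3.3 disagree on when to restart and at what dose, and the rule for unrelated events adds a third answer when attribution changes. Sites may therefore act differently on the same event.

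The hyponatremia conflict would concern about 10 of 40 patients if the pooled 24% carried over. The size of the neutropenia conflict cannot be derived from the documents.

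A reader might go on to conclude that tolerability becomes uninterpretable. That is not supported. The safety objective rests on the type, frequency, severity, timing and relatedness of adverse events (Protocol Section 2.2). Exposure is only summarized descriptively, and Section 6.3 requires every modification or delay to be recorded with its reason. Nor is the primary response analysis shown to change. The effect is on consistent patient handling and on per-protocol classification.

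**What to change.** Reconcile the Table 3 hyponatremia rows with Section 6.3.4. Reconcile the Table 3 neutropenia row, the rule after Table 3 for unrelated Grade 3 or higher events, and Section 6.3.3. Each event should end with one stated governing instruction covering the hold, the restart condition and the restart dose. The choice of clinical rule belongs to the sponsor's clinical team.

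For patients already treated, the data review meeting should record, before database lock, how actions that followed either passage are classified for the per-protocol set. The SAP addendum shows that an initial analysis has already been run. If the lock has passed, the classification used should be stated in the study report.

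The cost is a few sentences in an amendment or clarification letter and one entry in the subject classification document. No new procedures or patients are needed.
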